### 7.2 Dose and treatment regimens

The investigational medicinal product, anifrolumab 300 mg or placebo, will be administered via controlled IV infusion pump into a peripheral vein over a minimum of [REDACTED] Q4W from Week 0 to Week 48 for a total of 13 doses. **Each dose must be at least 14 days apart.**

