**Angioedema:** Angioedema is a self-limited, localized swelling of subcutaneous (or submucosal) tissue that results from extravasation of fluid into interstitial tissues. It presents with rapid, localized swelling, large welts, and pain. The lips, mouth, throat, eyes, hands, and feet are most commonly affected. Rarely, angioedema can be life-

threatening when swelling of the throat interferes with breathing. Angioedema may be acute or chronic (eg, hereditary angioedema), may occur with or without urticaria (hives), and is generally self-limited ([James and Bernstein 2017](#)).

Angioedema may be associated with IgE and may infrequently be a component of an anaphylactic reaction. In the absence of confirmatory IgE antibody, the Sampson Criteria should be used as the case definition for anaphylaxis.

Angioedema may be the result of histamine activation (often associated with urticaria), bradykinin generation, or unknown pathophysiology. The clinical presentation of these types of angioedema may be analogous in nature, but their treatment algorithms differ significantly.

**Infusion-related Reaction:** Infusion-related reactions are any other reaction occurring during infusion of study intervention or felt to be temporally related to the infusion within 24 hours of study intervention administration.

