Cutaneous Localized*	Yes	No	[≤ 3 contiguous unilateral dermatomes selected]
Cutaneous Disseminated	Yes	No	[> 3 contiguous unilateral dermatomes selected] or [non-contiguous dermatomes selected] or [dermatomes on left and right selected and/or bilateral selected]
Visceral Disseminated	Yes/No	Yes	[No rule]

* Cutaneous Localized is defined as below:

- CUTANEOUS/SKIN INVOLVEMENT = “YES”
- All affected dermatomes must be either “RIGHT” or “LEFT” not a mix of either or “BOTH”
- No more than 3 dermatomes are affected
- There is no other organ involvement
- There is an unbroken chain of affected dermatomes in the order that is presented in the image below.
 - The order is: V2, [(V1, V3) or (V3, V1) or (V1) or (V3)], C2, C3, C4, C5, C6, C7, C8, T1, T2, T3,... – T12, L1 – L5, S1 – S5

Adverse events during treatment are also presented by time intervals of the first onset of the event. For this analysis, repeated events with the same PT are not considered (i.e., if a participant has more than one event with the same PT, only the event with the earliest date of onset is used). For partial or missing dates, the rules as described above are used, i.e., the AE is considered as an AE during treatment unless the available information indicates otherwise and as occurring in the earliest possible time interval given the available (start and stop) date information. The following time intervals are defined:

- Day 1 to < Week 12:
AEs with date of onset \geq date of first administration of IP and < date of first administration of IP plus 84 days
- Week 12 to < Week 24:
AEs with date of onset \geq date of first administration of IP plus 84 days and < date of first administration of IP plus 168 days
- Week 24 to < Week 36:
AEs with date of onset \geq date of first administration of IP plus 168 days and < date of first administration of IP plus 252 days
- Week 36 to < Week 48:
AEs with date of onset \geq date of first administration of IP plus 252 days and < date of first administration of IP plus 336 days
- \geq Week 48:
AEs with date of onset \geq date of first administration of IP plus 336 days

Exposure-adjusted incident rate (EAIR) per 100 patient years is defined as

Sum of subjects with the event/[sum across subjects' time at risk for the event
/(365.25*100)]

Where time at risk is time to first event for subjects who experienced the event during the analysis period and time during the analysis period for subjects who do not experience the event.

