The time to first onset of an event during a specified period is derived as date of first onset of the event during the specified period – date of first administration of study intervention + 1. Only AEs with an onset date during specified period will be counted. If a subject has no such event during the specified period, the time to first onset is censored at the end date of the period.

The time during the analysis period for subjects who do not experience the event will be calculated as end of period – start of period + 1 (e.g., date of last dose of IP + 28 days - day of first dose of IP + 1 day for summary of AEs during treatment period; date of last dose of IP + 84 days - day of first dose of IP + 1 day for summary of AEs during treatment and follow-up period). If a participant discontinued from the study during a period or had the last follow-up visit earlier than expected, the date of study discontinuation/end of study will be used as end of the respective period.

For the by timepoint analysis of anaphylaxis, hypersensitivity, and infusion related reactions, an AE at a visit is defined as an AE with a date of onset \geq day of administration of IP at the respective visit and \leq date of administration of IP at the following visit (or \leq date of last dose of IP + 28 days for the last visit with IP).

Other significant adverse events

During the evaluation of the AE data, a medically qualified expert will review the list of AEs that were not reported as serious AE (SAEs) or AEs leading to discontinuation.

Based on the expert's judgment, significant AEs of particular clinical importance may, after consultation with the AstraZeneca Global Patient Safety Physician, be considered other significant AEs and reported as such in the CSR.

Examples of these are marked hematological and other laboratory abnormalities, and certain events that led to intervention (other than those already classified as serious), dose reduction, or significant additional treatment.

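### The by-visit window for infusion reactions in SAP 4.6.2.1 includes the next dose date, so an event starting on the day of infusion 2 to 13 is assigned to two visits

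*SAP*

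**What the plan says.** SAP section 4.6.2.1 gives one rule for the by-timepoint analysis of three event types: "For the by timepoint analysis of anaphylaxis, hypersensitivity, and infusion related reactions, an AE at a visit is defined as an AE with a date". The event must start no earlier than the dosing day of the visit in question and no later than the "date of administration of IP at the following visit". For a participant's final infusion the upper limit is instead the "date of last dose of IP + 28 days for the last visit with IP", also inclusive. The rule works on dates. It has no time-of-day condition and no instruction for an event that meets the definition for two visits.

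The 12-week onset intervals in the same section are built differently. The first ends with "and < date of first administration of IP plus 84 days", and the next begins on that day, so each date falls in one interval. The screening period likewise stops strictly before the first dose.

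Protocol section 7.2 sets the dosing: "Q4W from Week 0 to Week 48 for a total of 13 doses". Protocol Appendix S describes infusion-related reactions as arising during the infusion or judged "temporally related to the infusion within 24 hours of study intervention administration".

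**The concern.** Consecutive visit windows share one day, and that day is an infusion day. A reaction that starts on it is placed under the infusion just given and also under the infusion four weeks earlier, which for a reaction during the infusion is the wrong one. Same-day onset is an expected pattern for these events: Appendix S includes reactions during the infusion, and Protocol section 7.2.4 requires monitoring during each infusion and for at least 1 or 2 hours afterwards.

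What is at stake is attribution by visit. Each visit except the last picks up the same-day reactions of the next infusion. Anyone reading the output across visits would see the earlier figures raised and any change from one infusion to the next blurred. Hypersensitivity, anaphylactic reaction and infusion-related reaction are listed as identified risks in Protocol section 1.3, so the by-visit figures should be right even though they are descriptive.

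**Working it through.** **Inputs.** Window bounds: SAP 4.6.2.1. Number and spacing of infusions: Protocol 7.2 (13 infusions, every 4 weeks). The plan states no figure to reproduce.

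**Windows as written.** Let d(k) be the date of infusion k, counting the first as day 0, so d(k) = 28 × (k − 1): 0, 28, ..., 336.

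- Visits 1 to 12: d(k) ≤ onset ≤ d(k+1)
- Visit 13: d(13) ≤ onset ≤ d(13) + 28

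The date d(k+1) is the upper end of window k and the lower end of window k+1, so it satisfies both.

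**One same-day reaction at each infusion.**

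| Infusion | Visits assigned, upper bound ≤ (as written) | Visits assigned, upper bound < |
|---|---|---|
| 1 | 1 | 1 |
| 2 | 1 and 2 | 2 |
| 3 | 2 and 3 | 3 |
| ... | ... | ... |
| 13 | 12 and 13 | 13 |
| Total assignments | 1 + 12 × 2 = 25 | 13 |

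**All dates from day 0 to day 364 (365 dates).** As written, 12 dates fall in two windows, and all 12 are the dates of infusions 2 to 13; no date is left out. With a strict upper bound for visits 1 to 12, no date falls in two windows and none is left out. An onset on the day after an infusion falls in one window under either rule.

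The overlap does not depend on exact 28-day spacing, because it follows from the closed bounds on the actual dose dates. A participant who receives m infusions has m − 1 shared dates.

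**Effect on a visit figure.** Let r1 and r2 be the proportions with a same-day reaction at infusions 1 and 2, and r12 the proportion with one at both. If participants are counted, the same-day part of the first-visit figure is

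r1 + r2 − r12, where it should be r1.

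If events are counted, r12 is not subtracted. The same holds for each later pair of visits. Visit 13 gains nothing, because no infusion follows it.

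**The case against.** The literal overlap is hard to dispute; the case against concerns how much it matters.

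- **Scope.** SAP 4.6.2.2 summarises these reactions as participants with at least one event, overall and by seriousness, discontinuation and intensity. Neither those counts nor the exposure-adjusted rates use this window. Safety is descriptive, the rule is the same in both arms, and no decision depends on it. All of this stands.
- **Purpose of the output.** SAP 4.6.2.2 describes no by-infusion table and no comparison of the first infusion with later ones. A reader might infer that such a comparison is planned and would be spoiled. The documents do not say so. They define a by-timepoint analysis and leave its layout and counting unit open.
- **Doubling.** A reader might infer that every visit from 1 to 12 would show twice the true rate. That requires every reaction to start on the dose date, equal rates at all infusions, unchanged denominators, and either event counting or nobody reacting at consecutive infusions. The documents support none of these as facts. Appendix S allows onset within 24 hours for infusion-related reactions and usually within 48 hours for hypersensitivity, and SAP 4.6.2.1 identifies hypersensitivity by coded terms with no timing condition. If participants are counted, a duplicate adds nothing where that participant already has the same reaction type at the earlier visit.
- **A programmer would correct it.** Possibly, but the code would then depart from the SAP. Code that follows the SAP assigns the event twice.

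**Conclusion.** The rule is wrong as written, within a narrow scope. An event starting on the date of infusion 2 to 13 is assigned to its own visit and to the preceding one. The preceding visit's figure is raised by the next infusion's same-day reactions: for the first infusion, about r1 + r2 less participants reacting at both. The absolute size cannot be computed, because the infusion-reaction frequencies in Protocol section 1.2.4 are blacked out and no other usable rates are given. The 12 shared dates are a count of infusion dates, not a share of events.

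It would be a mistake to conclude that the product's overall reaction profile will be misreported: the planned overall counts and exposure-adjusted rates are unaffected. The conclusion assumes only that the by-timepoint analysis defined in 4.6.2.1 is produced and that its window is programmed as stated.

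**What to change.** In SAP 4.6.2.1, for every visit except the last with IP, define the window as onset on or after the dose date of that visit and strictly before the date of IP administration at the following visit. Keep last dose plus 28 days, inclusive, for the last visit with IP. This is a change to one bound in the SAP and the matching line of code; it needs no new data and agrees with the other onset intervals in the section. Protocol section 8.1 allows SAP amendments up to unblinding.

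An optional refinement covers an event that began on an infusion day before the infusion started, which the date-only rule would place under that day's infusion. Where both the onset time and the infusion start time are recorded and onset came first, assign the event to the previous visit. If either time is missing, assign it to the infusion given that day. This costs more than the bound change. Onset time is among the variables collected for each AE (Protocol section 6.4.3), but it must be compared with the infusion start time, which Protocol section 7.2.6 requires in the source document and which would have to be available in the database.

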4.6.2.2 Presentation

If not stated otherwise, all summaries described below are presented separately for

- AEs during treatment period
- AEs during treatment and follow-up period.

An overall summary of participants with at least one AE in the following categories is presented.

- Any AE
- Any SAE with outcome = death
- Any SAE (including events with outcome = death)
- Any AE leading to discontinuation of IP
- Any AE related to IP
- Any AE of severe intensity
- Any AESI
 - Any AESI of serious non-opportunistic infections
 - Any AESI of opportunistic infections
 - Any AESI of herpes zoster
 - Any AESI of tuberculosis including latent tuberculosis
 - Any AESI of malignancy
 - Any AESI of major adverse cardiovascular events (MACEs)
- Any other significant AE.

If not stated otherwise, the number and percentage of participants with at least one AE (i.e., multiple occurrences of an AE in 1 participant will only be counted once) are summarized by MedDRA primary SOC and PT for the following AE categories. If not stated otherwise, the EAIR per 100 patient years will be presented for AEs during treatment. A 95% confidence interval for the difference between Anifrolumab and Placebo will also be constructed based on Mienttinen and Nurminen method (Liu et. al., 2006). EAIR will generally not be included in summaries presented for AEs during treatment and follow-up period.

- Any AE
- Any AE above reporting threshold of 2%

This summary is presented by PT.

- Any SAE with outcome = death

This summary is presented for AEs during treatment and follow-up period only. This summary will not include the EAIR per 100 patient years.

- Any SAE (including events with outcome = death)

- Any AE leading to discontinuation of IP

This summary is presented for all AEs during treatment period only.

- Any AE by relationship to IP (yes, no)

(Multiple occurrences of an AE in 1 participant will only be counted once as related if at least one AE is related and as not related if all occurrences are not related).

This summary is presented for AEs during treatment and follow-up period only and will not include the EAIR per 100 patient years.

- Any AE by maximum intensity (mild, moderate, severe)

(Multiple occurrences of an AE in 1 participant will only be counted once with the maximum intensity in this AE).

This summary is presented for AEs during treatment and follow-up period only and will not include the EAIR per 100 patient years.

- Any AESI

This summary will not be presented by SOC but by AESI category

(Serious non-opportunistic infections, opportunistic infections, herpes zoster, tuberculosis including latent tuberculosis, malignancy and MACEs [Cardiovascular outcome events are reported by investigators]).

- Any other significant AE

This summary is presented for AEs during treatment and follow-up period only. This summary will not include the EAIR per 100 patient years.

- Any AE by time interval for the first onset of event

This summary is presented for AEs during treatment period only. This summary will not include the EAIR per 100 patient years.

The time to first onset of a serious non-opportunistic infection during treatment period and time to first onset of herpes zoster during treatment period is presented as Kaplan-Meier plots including the number of participants at risk at each visit.

Furthermore, the number and percentages of subjects with herpes zoster (and possible other AESIs) are summarized for events during treatment and follow-up period, during treatment period (overall and by time intervals). The following subcategories are also considered in this summary: SAE (including events with outcome of death), AE leading to discontinuation of IP, and AE by maximum intensity (mild, moderate, and severe).

The number and percentage of participants with at least one anaphylaxis, hypersensitivity, and infusion-related reaction (as reported by the investigator), respectively, is summarized overall as well as for the following respective subcategories: SAE (including events with outcome of death), AE leading to discontinuation of IP, and AE by maximum intensity (mild, moderate, and severe).

Infections, opportunistic infections and serious non-opportunistic infections, are summarized with the same subcategories as given above.

Key subject information for participants with an AE with outcome of death, participants with serious AEs, participants with an AE leading to discontinuation of IP, participants with AESIs, and ADA positive participants with AEs, respectively, is provided during treatment and follow-up period.

4.6.3 Clinical Laboratory

4.6.3.1 Definition and Derivations

The parameters of haematology, serum chemistry, urinalysis and of fasting lipid profile (high density lipoprotein cholesterol, low density lipoprotein cholesterol, and triglycerides) are explored.

Laboratory data are reported in international system of units (SI). Changes from baseline in haematology, clinical chemistry, urinalysis and lipid profile variables are calculated.

Absolute values are compared to the reference range as given in Appendix 1.1 and classified as low (below range), normal (within range or on limits) or high (above range). All values (absolute and change) falling outside the reference ranges are flagged.

Treatment emergent laboratory changes (TELVC) are defined for post-baseline values according to the reference ranges given in Appendix 1.1.

Urinalysis data are categorized as negative (0), positive (+), or strongly positive (++, +++, or >+++)) at each time-point.

For the liver function tests: aspartate transaminase (AST), alanine transaminase (ALT), Alkaline phosphatase, gamma glutamyl transferase (GGT) and total bilirubin, the multiple of the upper limit of the normal (ULN) range (see Appendix 1.1) are calculated for each data point. Multiple = Value / ULN, i.e., if the ALT value was 72 IU/L (ULN = 36) then the multiple would be 2. Participants meeting both of the following biochemical criteria for Hy's law (potential Hy's Law) at any point during the study (not necessarily at the same time) are flagged:

- AST ≥ 3 x ULN and/or ALT ≥ 3 x ULN
- Total bilirubin ≥ 2 xULN

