#### Medical Conditions

1. History of, or current diagnosis of, a clinically significant non-SLE related vasculitis syndrome (see [Appendix J](#)). Vasculitis due to SLE is allowed in the study.
2. History or evidence of suicidal ideation (severity of 4 [active: method and intent, but no plan] or 5 [active: method, intent, and plan]) within the past 6 months; or any suicidal behavior within the past 12 months or recurrent suicidal behaviour in the lifetime of the participant based on an assessment with the C-SSRS ([Appendix Q](#)) at screening or at baseline.
3. Active severe or unstable neuropsychiatric SLE including, but not limited to aseptic meningitis; cerebral vasculitis; myelopathy; demyelination syndromes (ascending, transverse, acute inflammatory demyelinating polyradiculopathy); acute confusional state; impaired level of consciousness; psychosis; acute stroke or stroke syndrome; cranial neuropathy; status epilepticus; cerebellar ataxia; and mononeuritis multiplex:
  - (a) Where, in the opinion of the Principal Investigator (PI), delegated Sub-Investigator (SI) or Sponsor, protocol specified standard therapy is insufficient and utilization of a more aggressive therapeutic approach, such as adding IV cyclophosphamide and/or high dose IV pulse corticosteroid therapy or other treatments not permitted in the protocol, is indicated.
4. Active severe SLE-driven renal disease where, in the opinion of the PI or delegated SI or Sponsor, protocol specified standard therapy is insufficient and utilization of a more aggressive therapeutic approach, such as adding IV cyclophosphamide and/or high dose IV pulse corticosteroid therapy or other treatments not permitted in the protocol, is indicated.
5. Diagnosis (within 1 year of signing the ICF) of mixed connective tissue disease or any history of overlap syndromes of SLE and systemic sclerosis (SSc), as noted in (a) or (b) below:
  - (a) An overlap syndrome of SLE with myositis or rheumatoid arthritis at Screening is permitted provided the participant also meets the criteria for the classification as SLE; or
  - (b) A history of mixed connective tissue disease, which over time has developed into a diagnosis of SLE, is permitted provided diagnosis of SLE has been present for at least 1 year.

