#### Laboratory Assessments

33. At Screening (within 35 days of randomisation), any of the following (note: retesting of laboratory test results during Screening may be repeated once):

- (a) Aspartate aminotransferase (AST)  $> 2.0 \times$  upper limit of normal (ULN).
- (b) Alanine aminotransferase (ALT)  $> 2.0 \times$  ULN.
- (c) c
- (d) Serum creatinine  $> 2.0$  mg/dL (or  $> 181 \mu\text{mol/L}$ )
- (e) Urine protein/creatinine ratio  $> 2.0$  mg/mg (or  $> 226.30$  mg/mmol)
- (f) Neutrophil count  $< 1000/\mu\text{L}$  (or  $< 1.0 \times 10^9/\text{L}$ )
- (g) Platelet count  $< 25000/\mu\text{L}$  (or  $< 25 \times 10^9/\text{L}$ )
- (h) Hemoglobin  $< 8$  g/dL (or  $< 80$  g/L), or  $< 7$  g/dL (or  $< 70$  g/L) if related to participant's SLE such as in active hemolytic anemia
- (i) Glycosylated hemoglobin (HbA1c)  $> 8\%$  (or  $> 0.08$ ) at Screening (diabetic participants only)

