4.6.3.2 Presentation

Observed values and changes from baseline of laboratory data for haematology, clinical chemistry, continuous urinalysis, and fasting lipid profile are summarized by visit. The summary statistics presented are minimum, 1st quartile, median, 3rd quartile, maximum, mean, and SD.

For each laboratory parameter with available criteria, the number and percentage of participants with TELVC values are summarized. Additionally, the number and percentage of participants with at least one TELVC value are presented. Percentages are based on participants with a measurement at baseline and at least 1 subsequent measurement of the variable.

The number and percentage of participants with laboratory values below, within or above the corresponding reference ranges are presented as shift tables from baseline to maximum and minimum on-treatment value, respectively.

Urinalysis is summarized as shift tables from baseline categorization to the last post-baseline value categorization for each parameter. Furthermore, the number and percentage of participants with treatment-emergent changes are summarized by parameter. Percentages for the summary of treatment emergent changes are based on participants with a measurement at baseline and at least 1 subsequent measurement of the variable. The three parameters Urine Glucose, Ketone Bodies and qualitative Erythrocytes should be added for presentation of TELVC for urinalysis. The criteria for TELVC for urinalysis data are defined as follows:

- Negative/positive at baseline to ++, +++, +++++ at any post-baseline value OR,
- Increase from baseline of at least ++ at any post-baseline value.

In order to identify potential Hy's Law cases, maximum on-treatment ALT and AST are summarized as number and percent versus maximum on-treatment total bilirubin.

All clinical safety laboratory data is listed, and any out-of-range laboratory measurements are flagged in the listing.

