4.6.5 Vital signs

4.6.5.1 Definition and Derivations

The following variables will be explored:

- Pulse (beats per minute)
- Systolic blood pressure (mmHg)
- Diastolic blood pressure (mmHg)
- Respiration rate (breaths per minute)
- Body temperature (°C)
- Body weight (kg)

Changes from baseline will be calculated.

Where applicable, absolute values are compared to the reference ranges given in Appendix 7.3 and classified as low (below range), normal (within range or on limits) or high (above range). All values (absolute and change) falling outside the reference ranges will be flagged.

Post-baseline values are classified as TELVC according to reference ranges given in Appendix 7.3.

For infusion visits, only measurements before start of IP are considered for by visit presentations. In case of multiple measurements before the start of IP, the first measurement is used for by visit presentations, but all measurements will be considered for the TELVC classification.

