7.2 Appendix B - Reference Ranges and TELVC for Laboratory Values

Parameter	Unit	Low value	Low decrease	High value	High increase
Haematology					
Hemoglobin	g/L	≤60	NA	≥200	NA
		≤70 and decrease from BL ≥15			
Hematocrit	V/V	≤0.18	NA	≥0.64	NA
		≤0.21 and decrease from BL ≥15%			
WBC	10E9/L	≤2, <1	NA	≥20	NA
Neutrophils	10E9/L	<0.5	NA	≥20	NA
		<1.0 and decrease from BL ≥0.5			
Lymphocyte	10E9/L	≤0.5, ≤0.25	NA	≥10.0	NA
Monocytes	10E9/L	NA	NA	≥1.4, ≥5.0	NA
Eosinophils	10E9/L	NA	NA	≥1.5, ≥5.0	NA
Basophils	10E9/L	NA	NA	≥1.0, ≥2.0	NA
INR		NA	NA	≥4.5	NA
Platelet	10E9/L	≤20	NA	≥600	NA
		≤50 and decrease from BL ≥25			
Biochemistry					
ALT	IU/L	NA	NA	≥3 x ULN, ≥5 x ULN	NA
AST	IU/L	NA	NA	≥3 x ULN, ≥5 x ULN	NA
ALP	IU/L	NA	NA	≥3 x ULN NA	NA
CK	IU/L	NA	NA	≥500, ≥2000	NA
GGT	IU/L	NA	NA	≥5 x ULN	NA
Total bilirubin	μmol/L	NA	NA	≥2 x ULN	NA
Albumin	g/L	≤20	NA	≥100	NA
		≤25 and decrease from BL ≥10		≥70 and increase from BL ≥10	
BUN	mmol/L	NA	NA	≥18	NA

Creatinine	umol/L	NA	NA	≥140, ≥190	NA
Sodium	mmol/L	≤132	NA	≥152	NA
Potassium	mmol/L	≤3	NA	≥5.5	NA
Chloride	mmol/L	≤90	NA	≥120	NA
Fasting Glucose	mmol/L	≤2.5	NA	≥7.0, ≥11.1	NA
Total Cholesterol	mmol/L	NA	NA	≥7.25	NA
Urinalysis					
Ketone Bodies/ Qualitative Erythrocytes/ U- Glucose					Negative/positive at baseline to ++, +++, +++++ at any post- baseline value Increase from baseline of at least ++ at any post-baseline value
Urine protein/ creatinine ratio	g/mmol	NA	NA	≥0.395	NA
Urine protein					Increase ≥ ++ ≥ ++ with BL negative, TRACE, or +
Fasting lipid profile					
HDL	mmol/L	≤0.8	NA	NA	NA
LDL	mmol/L	NA	NA	≥5.2	NA
Triglycerides	mmol/L	NA	NA	≥3.6, ≥5.4	NA

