7.3 Appendix C - Reference Ranges and TELVC for Vital Signs

Parameter	Unit	Low value	Low decrease	High value	High increase
Pulse	Beats per minute	≤ 50 ≤ 50 and decrease from BL ≥ 20	NA	≥ 120 ≥ 120 and increase from BL ≥ 20	NA
Systolic blood pressure	mmHg	≤ 90 ≤ 90 and decrease from BL ≥ 20	NA	≥ 160 ≥ 160 and increase from BL ≥ 20	NA
Diastolic blood pressure	mmHg	≤ 50 ≤ 50 and decrease from BL ≥ 10	NA	≥ 100 ≥ 100 and increase from BL ≥ 10	NA

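### For many laboratory limits and the bare vital-sign limits, a value already abnormal at baseline and unchanged afterwards is counted as treatment-emergent

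*SAP*

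**What the plan says.** **Definition.** SAP 4.6.3.1 (laboratory): "Treatment emergent laboratory changes (TELVC) are defined for post-baseline values according to the reference ranges given in Appendix 1.1". SAP 4.6.5.1 (vital signs): "Post-baseline values are classified as TELVC according to reference ranges given in Appendix 7.3". Neither section, nor any other part of the SAP, adds a general rule that the value must be new or worse than at baseline.

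**Denominator.** SAP 4.6.3.2: "Percentages are based on participants with a measurement at baseline and at least 1 subsequent measurement of the variable". SAP 4.6.5.2 has the same rule. A baseline value must exist, but it need not be on the acceptable side of the limit.

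**Limits.** SAP Appendix B (7.2) gives most analytes one or two absolute cut-offs. Some criteria do use baseline: haemoglobin has "≤70 and decrease from BL ≥15", there are similar second-tier limits for haematocrit, neutrophils, platelets and albumin, and dipstick urinalysis has "Negative/positive at baseline to ++, +++, +++++ at any post-baseline value". In Appendix C (7.3) each pulse and blood-pressure limit appears twice, once bare and once with a change from baseline, for example ≥160 mmHg systolic and "≥ 160 and increase from BL ≥ 20".

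**Entry.** Protocol 3.2, criterion 33(d) excludes on "Serum creatinine" only above 181 µmol/L. Criterion 33 lists no limit for lymphocytes, WBC, CK or fasting glucose (HbA1c above 8% excludes diabetic participants only), and no criterion limits blood pressure. Criterion 5(a) adds: "An overlap syndrome of SLE with myositis or rheumatoid arthritis at Screening is permitted".

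**The concern.** A count labelled treatment-emergent should show what appeared or worsened after dosing began. In SLE, low lymphocytes, low white cells and raised creatinine can be long-standing. A participant who enters with creatinine of 150 µmol/L and stays there meets the ≥140 criterion at the first post-baseline visit with no change at all. Such participants are expected in similar numbers in both arms. They raise both reported percentages and make the arms look more alike in relative terms. The tables at stake are the TELVC summaries for the exposed analytes and for pulse and blood pressure.

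**Working it through.** The documents give no TELVC rate and no baseline prevalence, so there is no planned figure to reproduce. The check has two parts.

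**1. Which limits are exposed.** Each criterion in Appendices B and C was classed as absolute or baseline-conditioned, then compared with exclusion criterion 33.

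| | Criteria | Absolute | Baseline-conditioned | Absolute, blocked at screening | Absolute, open |
|---|---|---|---|---|---|
| Appendix B | 60 | 50 | 10 | 10 | 40 |
| Appendix C | 12 | 6 | 6 | 0 | 6 |

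The ten blocked limits are:
- haemoglobin ≤60 g/L (entry limit 80, or 70 if SLE-related);
- neutrophils <0.5 (entry limit 1.0), which also blocks WBC <1;
- platelets ≤20 (entry limit 25);
- ALT and AST at ≥3 and ≥5 × ULN (entry limit 2 × ULN), four criteria;
- creatinine ≥190 µmol/L (entry limit 181);
- urine protein/creatinine ≥0.395 g/mmol (entry limit 226.30 mg/mmol = 0.226 g/mmol).

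Among the 40 open limits are creatinine ≥140 (values from 140 to 181 may enter), lymphocytes ≤0.5 and ≤0.25, WBC ≤2, CK ≥500 and ≥2000, and fasting glucose ≥7.0 and ≥11.1. Some of the 40 are unlikely to be met at entry in practice. Criterion 33(c) is unreadable in the available text, so nothing is concluded about bilirubin, which is counted as open. The counts depend on how the tables were extracted.

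**2. Effect on the reported rates.** Let b be the share of each arm that meets the limit at baseline and again afterwards, and p the new-onset rate among the rest.

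- Reported rate = b + (1 − b)p
- Reported difference = (1 − b)(p₁ − p₀)
- Reported ratio = [b + (1 − b)p₁] / [b + (1 − b)p₀], which moves towards 1 as b rises

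Both b and p below are assumptions.

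| p₀ vs p₁ | b | Reported rates | Ratio | Difference (points) |
|---|---|---|---|---|
| 3% vs 6% | 0 | 3.0% vs 6.0% | 2.00 | 3.0 |
| | 2% | 4.9% vs 7.9% | 1.60 | 2.94 |
| | 10% | 12.7% vs 15.4% | 1.21 | 2.7 |
| | 15% | 17.6% vs 20.1% | 1.15 | 2.55 |
| 10% vs 20% | 0 | 10.0% vs 20.0% | 2.00 | 10.0 |
| | 5% | 14.5% vs 24.0% | 1.66 | 9.5 |
| | 10% | 19.0% vs 28.0% | 1.47 | 9.0 |
| | 20% | 28.0% vs 36.0% | 1.29 | 8.0 |
| | 30% | 37.0% vs 44.0% | 1.19 | 7.0 |

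In counts, with 130 per arm and b = 10%, 13 participants in each arm are pre-existing cases. At p₀ = 3% the new cases number 117 × 0.03 = 3.5, so 13 of the 16.5 counted were present before dosing. Removing the 13 from numerator and denominator restores the ratio of 2.00 on 117 per arm.

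**The case against.** **Other tables show baseline status.** SAP 4.6.3.2 and 4.6.5.2 plan shift tables from baseline to the on-treatment extremes (laboratory values; pulse and blood pressure), plus changes from baseline by visit. Listings flag out-of-range laboratory values. A reader might infer that the TELVC tables are the only view of these signals; they are not. The relief is partial, however. The shift tables use low/normal/high categories, so a participant below the normal range at baseline who later crosses a TELVC limit stays in the low-to-low cell. Their laboratory source is also unclear: 4.6.3.1 names Appendix 1.1 for both the ranges and the TELVC limits, no such appendix exists, and Appendix B contains limits but no normal ranges.

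**Many limits are sound.** A reader might infer that every TELVC is contaminated. The blocked and baseline-conditioned limits above contradict that, with the small reservation that exclusions apply at screening while baseline is Day 1, up to 35 days later.

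**Appendix C may already hold the right row.** Each threshold-plus-change limb is a subset of its bare limit. It is therefore tempting to call the change limbs inert. That follows only if the two are merged so that either triggers the flag, and the SAP does not say so. What stands is that their tabulation is unstated and that the bare limit carries no baseline condition.

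**Absolute counts have a use.** Protocol 8.5.3.1 plans frequencies of clinically noteworthy values, and absolute limits serve that purpose. This stands as a reason to keep such values visible, but not under a treatment-emergent label.

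**Conclusion.** The point holds for many laboratory analytes and for the bare vital-sign limits. Followed exactly, the SAP reports unchanged baseline abnormalities as treatment-emergent, because the definition, the denominator and the entry criteria all allow it. Wherever b is above zero and similar in both arms, the reported incidence is too high, the ratio moves towards 1 and the difference shrinks by 1 − b.

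The size cannot be taken from the documents. It rests on an assumed b, on those participants staying past the limit, and on assumed new-onset rates. A reader might take a ratio of 1.15 as the expected result, or conclude that a real signal would be hidden. Neither is supported: shares of 10% to 15% are illustrative for strict limits, permitting myositis overlap establishes no CK prevalence, and the difference falls only from 3.0 to between 2.7 and 2.55 points in those cases. SAP 4.6.3.2 and 4.6.5.2 plan counts and percentages, SAP 4.6 makes safety descriptive, and no TELVC test or ratio is planned. No efficacy conclusion is touched. The correction is worth making because it is specific and cheap.

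**What to change.** 1. In SAP 4.6.3.1 and 4.6.5.1, count a TELVC only when a post-baseline value meets a criterion that the participant's baseline value did not meet, or moves to the next stricter limit where two are listed. The limits themselves stay as they are.
2. In SAP 4.6.3.2 and 4.6.5.2, base each percentage on participants with a baseline and at least one later value whose baseline did not meet that criterion. A participant entering at creatinine 150 µmol/L then leaves the ≥140 row but stays in the ≥190 row.
3. In Appendix C, apply the same rule to the bare limit and report the threshold-plus-change limb as a separate row. Using the combined limb alone would miss a new crossing such as 150 to 165 mmHg.
4. Correct the three references to Appendix 1.1 in 4.6.3.1, and state where the normal ranges for the shift tables come from.
5. Keep all abnormal values in the listings.

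The cost is SAP wording and one derivation flag from data already held, to be settled before unblinding. One small downside is that worsening within a tier among participants already past the limit (for example WBC 1.9 to 1.1) is then seen only in the change-from-baseline summaries and the listings.
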